COMIRB 19-0402

PI: [name]

Version Date: December 6, 2023

SARC Approved 5/8/2019

***Per-oral Pancreatoscopy-guided Lithotripsy vs. Extracorporeal Shock Wave
Lithotripsy For Treating Symptomatic Main Pancreatic Duct Stones in Chronic
Pancreatitis: A Multicenter Randomized Clinical Trial***

Lead Site: University of Colorado

Version Date: December 6, 2023

Table of Contents

Table of Contents.....	2
Synopsis	3
List of Abbreviations	4
Study Protocol.....	5
Research Questions and Hypothesis	5
Basic Design of the Study	7
Sample and Methodology	7
Subject Inclusion and Exclusion Criteria	9
Inclusion Criteria:	9
Exclusion Criteria:	9
Study Steps	10
Screening/Baseline Evaluation	10
Consent	10
Randomization	10
Treatment Regimens	10
Outcome Determination	11
Standard of Care/Research Procedure.....	12
Subject and Study Stopping Criteria.....	12
Data Collection Tool	13
Data Analysis Plan	13
Data and safety monitoring plan.....	14
Definition of AEs, serious AEs, and unanticipated problems	14
Procedures for documentation of adverse events	15
Monitoring of Data	16
Feasibility/Recruitment Plan/Materials	16
Training Plan.....	16

Synopsis

Title	Per-oral Pancreatoscopy-guided Lithotripsy vs. Extracorporeal Shock Wave Lithotripsy in Chronic Pancreatitis: A Multicenter Randomized Clinical Trial
Investigative sites	University of Colorado The Ohio State University Baylor St. Luke's Medical Center Methodist Dallas Medical Center University of Minnesota University Health, San Antonio Indiana University Washington University School of Medicine
Hypothesis	The central hypothesis is that per-oral pancreatoscopy- guided lithotripsy is superior to extracorporeal shock wave lithotripsy in clearance of main pancreatic duct stones, thereby improving pain levels and quality of life in patients with chronic calcific pancreatitis.
Primary Objective	To demonstrate the superiority of per-oral pancreatoscopy over extracorporeal shock wave lithotripsy in clearance of main pancreatic duct stones in patients with chronic pancreatitis. Failure to remove any or all stones with the initial intervention will be an outcome recorded for the study.
Secondary Objective	To demonstrate the effect of stone clearance to reduce pain and opiate use and improve quality of life.
Timeline	Enrollment will be performed over a 24-month time period with follow-up performed at 1, 3, 6, 12, 18, and 24 months after ductal clearance.

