These methods, however, may be limited by imprecision, limited ESWL availability for PD stone therapy in the US, requirement of multiple treatment sessions, and decreased efficacy in removing larger, impacted stones.^{9, 10} From a practical standpoint, the need to frequently outsource ESWL to urologists limits the ability of gastroenterologists to control the timing of these sessions and assess efficacy while potentially increasing patient costs, time commitment, and use of general anesthesia.¹¹ If ineffective in stone clearance, surgery remains a last-resort option that is associated with high morbidity (18-53%) and mortality (0-4.55%).¹² The introduction of per oral pancreatoscopy, or direct endoscopic visualization of the PD, has enabled targeted intraductal therapy, including electrohydraulic lithotripsy (**EHL**) and laser lithotripsy (**LL**) for these stones.¹³ None of these treatment methods have been studied in prospective trials and there is a lack of comparative data between ERCP techniques and ESWL in removing stones, whether they improve pain and quality of life, and reduce opiate use along with assessing financial costs. There is, therefore, a *critical need* to compare the efficacy of per oral pancreatoscopy-guided lithotripsy (**PPL**) with ESWL and determine which therapy provides better outcomes with a goal of less procedures and that is more cost-effective in removing difficult PD stones. Without such information, the treatment of main pancreatic duct stones associated with chronic pancreatitis will likely remain limited anecdotal and consisting of retrospective case series.

Within the field of pancreatology, there exists legitimate equipoise regarding which treatment is more effective in removing pancreatic duct stones. ESWL has been performed for a longer period of time with a meta-analysis including 27 studies and 3189 patients demonstrating a 70% complete duct clearance rate with the use of ESWL.¹⁴ There have been far fewer studies involving PPL with a recent meta-analysis involving 302 patients in 10 studies found a 86% success rate in stone clearance.¹⁵ Importantly, a randomized study comparing the two techniques has not been performed and the only randomized study

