This study is a multicenter randomized trial comparing per oral pancreatoscopy-guided lithotripsy (**PPL**) using either laser lithotripsy (**LL**) or electrohydraulic lithotripsy (**EHL**) with extracorporeal shock wave lithotripsy (**ESWL**) in removing main pancreatic duct (**PD**) stones from patients with chronic calcific pancreatitis. Specific aims for this trial include:

- **SA1:** To determine whether PPL is more effective than ESWL in removing PD stones in terms of main pancreatic duct stone clearance rate in patients with chronic calcific pancreatitis.
- **SA2:** Evaluate the effectiveness of main pancreatic duct stone removal in reducing pain and improving quality of life in patients with chronic calcific pancreatitis.
 - **SA2a:** To determine whether a greater clearance of PD stones via PPL or ESWL will improve quality of life to a greater extent.
 - **SA2b:** To determine whether a greater clearance of PD stones via PPL or ESWL will reduce pain and opiate requirements to a larger extent.

The primary endpoint of this trial will be complete clearance of main PD stones in eligible patients. This study will be statistically powered to detect superiority of PPL over ESWL in this primary endpoint. Major secondary endpoints will include: 1) change in quality of life after PD stone removal; 2) change in pain levels after PD stone removal; 3) change in opiate use after PD stone removal; 4) comparison of total number of procedures in both arms, and 5) PD stone recurrence rate.

3. Sample and Methodology

We will enroll 150 subjects (**Figure 1**) with chronic pancreatitis who have symptomatic main PD stones identified by non-invasive imaging, endoscopic ultrasound or prior endoscopic retrograde pancreatography (**ERP**).

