Following baseline assessments and identification of main PD stones, patients will be randomly assigned to receive either PPL or ESWL as the primary lithotripsy method to fracture PD stones. Both these procedures represent potential next steps in the algorithm of managing PD stones.³ If partial clearance (removal of some, but not all stones) of PD stones is achieved as determined by the performing endoscopist, subjects can receive repeated PPL or ESWL sessions (for a maximum of 4 sessions total as is commonly practiced before referral for alternative therapy) until complete removal of stones is achieved.⁵ Failure to remove any main PD stones will be considered a failure of the treatment. Additionally, failure to achieve complete clearance within a maximum of 4 sessions of either PPL or ESWL will be considered a treatment failure, even if partial clearance is achieved.

Cross-over and/or combination therapy will be allowed at the discretion of the endoscopist after treatment failure. As described in the statistical analysis, under the intention-to-treat (primary) analysis, should cross-over occur, the final outcome of complete stone clearance will be attributed to the initial therapy. Under the per-protocol (secondary) analysis, in the case of cross-over, the final outcome of complete stone clearance will be attributed to the combination of ESWL and PPL. Similarly, in terms of survey collection, should cross-over occur, the analysis of the survey results will be attributed to the

originally assigned intervention in the intention-to-treat (primary) analysis. In the per-protocol (secondary) analysis, the outcomes will be attributed to the combination of both interventions resulting in technical success.

Patients who are randomized and subsequently found to have an exclusion criteria identified will continue follow-up per study protocol.

Stone clearance will be determined by occlusion pancreatography showing the absence of main PD stones. Complete stone clearance will be defined as the absence of stones in the head or body of the main PD. Partial stone clearance will be defined as the removal of more than 50% but less than 100% of stone/stone fragments in the head or body of the main PD.

[figure not shown]
Recurrence will be defined as the presence of stones following confirmed clearance in the final pancreatogram. To be considered as recurring, the stone must require intraductal lithotripsy for removal.

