Following complete PD stone removal, patients will be given a validated quality-of-life instrument, the PANQOL¹⁸, at 1, 3, 6, 12, 18, and 24 months post-treatment. Similarly, the visual analog scale will also be given at 1, 3, 6, 12, 18, and 24 months post-treatment. Lastly, daily opiate use will be recorded at 1, 3, 6, 12, 18, and 24 months post-treatment. The 1, 3, 6, 12, 18, and 24-month assessments will have a ± 2 weeks window to be completed.

In order to ensure that subjects respond to the questionnaires as required, REDCap will be programmed to automatically send three reminders to the participants' email when the questionnaires are due. Furthermore, the study coordinator will make three separate attempts to contact non-responding patients within the designated timeframe. If a patient remains unresponsive, these instances will be documented as protocol deviations.

Documentation on interventions for chronic pancreatitis occurring outside of scheduled appointments will be recorded a separate CRF ("non-scheduled chronic pancreatitis interventions"). This CRF will encompass any pancreatic interventions (other than POP x ESWL planned visits) taking place between the subject's consent form signature and their final follow-up.

All patients will have a HgbA1c and fecal elastase drawn at baseline (within 12 months prior to treatment initiation) and at the 1-year mark from treatment completion. Laboratory tests will be drawn per standard of care, and tests results will be added to the REDCap database.

Figure 1: Study Flowsheet

4. Subject Inclusion and Exclusion Criteria

4.1 *Inclusion Criteria:*

1. Subjects aged 18-89
2. Subjects with abdominal pain secondary to chronic calcific pancreatitis and main pancreatic duct stones found on cross-sectional imaging, EUS, or ERP with upstream PD dilation
3. Main PD stones in the head or body that are greater than 50% in size of the immediate downstream diameter of the pancreatic duct
4. Stones ≥ 5 mm in diameter or impacted in the main PD on cross-sectional imaging or EUS

4.2 *Exclusion Criteria:*

1. Subjects who have previously received PPL or ESWL for PD stones within 12 months of enrollment
2. Patients with PD stones isolated in the tail or side branches of the main duct
3. Pancreatic tail stones comprising more than one-third of the stone burden within the main PD, if multiple locations of stones are noted within the main PD
4. Nontraversable ansa loop with upstream stones

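### The quality-of-life schedule starts only after complete stone removal, which conflicts with the intention-to-treat and partial-clearance analyses planned on the same outcome

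*Combined protocol and SAP*

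**What the plan says.** **When outcomes are collected.** Section 3 introduces the PANQOL with "Following complete PD stone removal, patients will be given a validated quality-of-life instrument", at six visits from 1 to 24 months; the same sentence ends by counting those months post-treatment. The next two sentences put VAS pain and daily opiate use on the same months, dated only as post-treatment. The Synopsis (Timeline) applies a clearance anchor to the whole schedule: "follow-up performed at 1, 3, 6, 12, 18, and 24 months after ductal clearance". For the laboratory tests, by contrast, Section 3 refers to all patients and dates the one-year sample from completion of treatment.

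**How they are analysed.** Section 9 compares change in PANQOL, VAS and opiate dose between the PPL and ESWL groups, with intention to treat as the primary analysis. It adds a subgroup analysis of the same outcomes in patients with only partial clearance, whom it calls treatment failures. Section 3 allows cross-over after failure, at the endoscopist's discretion, and assigns the survey results of such patients to the original arm.

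**What is asked.** Aim SA2a in Section 2 is "To determine whether a greater clearance of PD stones via PPL or ESWL will improve quality of life to a greater extent"; SA2b puts the same question for pain and opiates. The listed secondary endpoint is "change in quality of life after PD stone removal".

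**Periods.** The Synopsis states "Enrollment will be performed over a 24-month time period", while Section 11 expects enrolment to take up to 5 years. Follow-up is 24 months in the Synopsis and Section 3, 12 months per patient in Section 11, and 6 months at study stop in Section 7.

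**The concern.** Complete clearance is the primary outcome, it is observed after randomisation, and the trial expects it to differ between arms. If the questionnaire clock starts only at clearance, the nominal intention-to-treat comparison of quality of life becomes a comparison of cleared ESWL patients with cleared PPL patients. Those groups are no longer protected by randomisation. The central hypothesis is that PPL improves pain and quality of life by clearing more stones, and that is exactly the effect that vanishes when everyone compared has been cleared.

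Two planned analyses would also lack data. The partial-clearance subgroup would have no scheduled PANQOL unless its members were later cleared. SA2a and SA2b ask whether more clearance brings more benefit, which needs outcomes from patients with less clearance. The SA2 headline and the secondary endpoint wording could be met from cleared patients alone, so the conflict lies with SA2a, SA2b and Section 9.

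**Working it through.** **1. The trigger against the analysis, by type of patient**

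| Patient | PANQOL start under Section 3 and Synopsis wording | Needed by Section 9 |
|---|---|---|
| Cleared by assigned treatment | At clearance | Arm comparison |
| Failed, then cleared after cross-over | At the later clearance | Arm comparison, in the assigned arm |
| Never cleared | None stated | Arm comparison, and the subgroup if clearance was partial |

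The third row is the gap. Section 3 does say that patients later found to meet an exclusion criterion continue follow-up; no visible sentence says so for treatment failures.

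**2. The plan's own figure.** Inputs from the power analysis in Section 9: 70% ESWL, 90% PPL, two-sided alpha 0.05, power 80%. With pooled variance under the null and mean rate 0.80:

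n = [1.96 × √(2 × 0.80 × 0.20) + 0.8416 × √(0.70 × 0.30 + 0.90 × 0.10)]² / 0.20² = (1.1087 + 0.4610)² / 0.04 = 61.6, so 62 per arm and 124 in total, as stated. The plan enrols 75 per arm; 20% dropout leaves 75 × 0.80 = 60.

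**3. Patients without a start date, before cross-over.** Uncleared = arm size × (1 − clearance rate).

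- 75 per arm: ESWL 75 × 0.30 = 22.5; PPL 75 × 0.10 = 7.5; total 30 of 150 (20%). This leaves 52.5 against 67.5 for the comparison.
- 60 per arm, if dropout is unrelated to clearance: 60 × 0.30 = 18; 60 × 0.10 = 6; total 24 of 120.

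With ESWL held at 70%, over the PPL rates in the document:

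| PPL rate | Source | PPL uncleared of 75 | Total of 150 | Total of 120 |
|---|---|---|---|---|
| 83% | Power analysis, low end | 12.75 | 35.25 | 28.2 |
| 86% | Section 1, "found a 86% success rate in stone clearance", taken as complete clearance | 10.5 | 33.0 | 26.4 |
| 90% | Planning value | 7.5 | 30.0 | 24.0 |
| 99% | Power analysis, high end | 0.75 | 23.25 | 18.6 |

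**4. Cross-over.** The document gives no rescue rate. If fractions rE and rP of the failures are later cleared, 22.5(1 − rE) and 7.5(1 − rP) remain at 75 per arm. Assumed values show the range:

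- 50% and 50%: 11.25 against 3.75 (smaller).
- 90% and 70%: 2.25 against 2.25 (no imbalance).
- 90% and 0%: 2.25 against 7.5 (reversed).

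**5. The effect that is lost.** Suppose clearance improves the outcome by g SD, the arms differ in no other way, and nobody crosses over. With everyone surveyed, the arm difference is g × (0.90 − 0.70) = 0.20g. Among cleared patients only, both arms carry the full g and the difference is zero. The value of g is unknown; the algebra shows only that the contrast disappears whatever it is.

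**The case against.** The strongest reply is that the document, read as a whole, means to survey everyone. The PANQOL sentence itself ends post-treatment. VAS and opiate use carry no clearance condition of their own. The laboratory tests cover all patients from treatment completion, and Section 11 counts follow-up per patient from completion of treatment. Section 3 says how to attribute surveys after cross-over, which happens only after failure, and Section 9 plans these outcomes in partial-clearance failures. Figure 1, the study flowsheet, cannot be seen and may settle the matter. Nor does any text say that REDCap fires on clearance; reminders go out when questionnaires are due.

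Most of this stands, and it makes a drafting conflict the likeliest explanation. It does not close the gap, because none of those places gives a never-cleared patient a PANQOL date, while the two places that set the schedule both name clearance. Cross-over is discretionary, so it cannot be relied on to supply a date, and when it does the date comes later.

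A reader might also infer that the partial-clearance subgroup is undefined, because Section 3 uses the term twice: "If partial clearance (removal of some, but not all stones) of PD stones is achieved" and "Partial stone clearance will be defined as the removal of more than 50% but less than 100% of stone/stone fragments". That goes too far. The second is a formal definition, and Section 9 uses its term; the first is a parenthesis about when sessions may be repeated. Only the parenthesis needs aligning.

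**Conclusion.** The concern holds as a conflict between the outcome schedule and the analysis, and it should be fixed; confidence is medium because Figure 1 is unseen. If the trigger is applied as written, about 30 of 150 patients (22.5 ESWL, 7.5 PPL) would have no scheduled PANQOL before cross-over, or 24 of 120 after the planned dropout. These counts rest on the plan's 70% and 90% clearance rates and, for the second, on dropout unrelated to clearance.

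Four stronger readings are not supported:

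- That failures will go unfollowed. The document points the other way in several places; it simply never schedules them.
- That pain and opiate use are expressly conditional on clearance in Section 3. The explicit condition there attaches to the PANQOL; for the other two it is arguable, through the Synopsis.
- That the comparison would favour a particular arm. The direction and size of any selection bias depend on rescue rates and patient differences that the document does not give.
- That the primary result is at risk. The primary endpoint, stone clearance, does not depend on the questionnaires.

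The differing follow-up and enrolment periods are a separate inconsistency. They need reconciling but add no weight to this one.

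**What to change.** 1. State in the Synopsis, Section 3 and Section 9 that PANQOL, VAS and daily opiate use are collected in all randomised patients, whatever their clearance or cross-over status. Set the REDCap trigger to match.
2. Define one time zero that exists for every patient in both arms, and say whether it falls before or after cross-over. There are two candidates, each with a drawback. The end of assigned treatment (clearance or declared failure) keeps the post-treatment wording, but its date varies with the number of sessions and early surveys may fall during rescue treatment. Randomisation does not depend on outcome, but early surveys may fall during treatment.
3. Reconcile the follow-up length (Synopsis, Sections 3, 7 and 11) and the enrolment period (Synopsis and Section 11). Align the Section 3 parenthesis on partial clearance with the formal definition.
4. Optionally, adjust the arm comparison for the baseline quality of life and pain that Section 5.1 already collects. This would gain precision; it does not correct the selection.

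The cost is a protocol amendment through the IRBs of the eight sites, a change to the REDCap trigger, and surveys for about 19 to 35 more patients before cross-over, using reminders already planned, with some extra coordinator contact. Keeping 24 months for every patient would also lengthen the study beyond what Section 11 foresees. Treatment and sample size do not change. If the sites already survey everyone, only the wording changes.

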5. Inability to place a transpapillary pancreatic duct stent during ERP
6. Patients with prior pancreatic surgery or surgically altered gastroduodenal anatomy, such as Roux-en-Y surgery

7. Acquired pancreas divisum
8. Significant cardiopulmonary co-morbidities precluding general anesthesia
9. Patients with coagulation disorders that cannot be corrected to an INR below 2.0
10. Patients with ongoing alcohol abuse and/or illicit drug use, except products containing THC
11. Pregnancy
12. Patients in active treatment for malignancy other than non-melanoma skin cancer or papillary thyroid cancer

5. Study Steps

5.1 *Screening/Baseline Evaluation*

Potential eligible patients will undergo an initial visit in which eligibility will be confirmed and the trial protocol explained in detail. All willing and eligible patients providing informed consent will have baseline data obtained including detailed history of chronic pancreatitis (i.e. disease duration, etiology, drug use, and family history of pancreatic disease), endoscopy history, and current medication use. Baseline quality of life and pain levels will also be obtained. Laboratory tests: HbA1c and Fecal elastase will be drawn per standard of care within 12 months prior to enrollment, and tests results will be documented in the study.

The National Institute of Alcohol Abuse and Alcoholism (NIAAA) defines binge drinking as a pattern of drinking alcohol that brings blood alcohol concentration (BAC) to 0.08 percent - or 0.08 grams of alcohol per deciliter - or higher. For a typical adult, this pattern corresponds to consuming 5 or more drinks (male), or 4 or more drinks (female), in about 2 hours.¹⁹

Patients of childbearing potential will undergo a serum/urine pregnancy test based on each site practice, as per the standard of care.

5.2 *Consent*

Patients will be provided the necessary information regarding the study and consent will be obtained either in person and/or electronically through medical records depending on specific site IRB approval guidelines. Consent for the study will be obtained by a member of the study team either in person or electronically through medical records depending on specific site IRB approval guidelines.

5.3 *Randomization*

Randomization will occur after informed consent is obtained and prior to receiving lithotripsy. Once enrolled, the research coordinator will enter the patient into the REDCap database, at which randomization will occur via computer algorithm.

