Randomization will be performed using a 1:1 ratio. The investigator will then inform the patient which lithotripsy therapy will be subsequently performed.

5.4 *Treatment Regimens*

Per oral pancreatoscopy-guided lithotripsy

Standard ERP will be performed to cannulate the PD, perform pancreatic sphincterotomy, and stricture

dilation as necessary. A panreatoscope (Spyglass Digital System, Boston Scientific, Marlborough, MA) will then be inserted through the duodenoscope into the PD. For PPL, electrical pulses will be delivered through an aqueous medium by EHL or LL with the probe tip in contact with or 1-2mm away from the stone.

For EHL, the Nortech bipolar biliary EHL probe (1.9 Fr, 0.66 mm) will be used and lithotripsy will start at medium power and can be increased to high power (maximum of 100 Joules). In terms of frequency, the maximum frequency allowed will be 30 pulses/second. There will be no limit to the number of EHL probes used during a session of lithotripsy, but the maximum time of lithotripsy allowed will be 1 hour.

For LL, Holmium laser will be utilized with energy ranging from 1 to 10.5 Joules, a frequency of 8-14 Hz and a power from 5-25W. LL fibers will include 200, 272, and 365 μ meter fibers. Similar to EHL, a maximum of 1 hour of intraductal lithotripsy will be allowed. Both forms of intraductal lithotripsy can be performed during the same treatment session.

EHL and/or LL will be continued until stone fragments are \leq 3 mm or a maximum of 1 hour of lithotripsy.

Extracorporeal shock wave lithotripsy

Stone localization will first be performed by obtaining high-quality plain films of the pancreatic area in left and right oblique positions using a two-dimensional radiologic targeting system.

Depending on the stone localization, ESWL will then be performed with the patient in either slight left or right lateral decubitus with shock waves entering the body from the ventral side. The shockwaves will be focused first on the most downstream located stone within the main duct and then on other calculi moving from the head towards the body. If a stent has been inserted during preceding ERP then this may also serve as a guide to target main pancreatic duct stones by ESWL.

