ESWL will start at the lowest power level and will gradually be increased until 25% of the shocks have been delivered to help create vascular constriction to minimize the risk of hematoma. The middle 50% of the shocks will be equally distributed between the 1st 25% of shocks and the final 25% of shocks at the top level of power. The final 1000 shocks should be administered at the highest power level number. The range of shocks delivered will be limited to 4000 to 6000 shocks. The rate of shocks will range from 70-90/minute.

A KUB (kidney-urether-bladder)-right posterior oblique X-ray will be done within 7 days after the ESWL session to determine the level of fragmentation of the stones. The goal will be to continue ESWL until stone fragments are felt to be \leq 3mm.

Non-lithotripsy panreatoscopy maneuvers will be permitted in the ESWL arm and not result in primary endpoint failure.

5.5 *Outcome Determination*

An occlusion panreatogram following extraction of stone fragments will be obtained after the endoscopist/urologist has determined treatment completion. All patients will receive an ERP at the completion or either PPL or ESWL, with an occlusion panreatogram performed to determine stone

clearance. An initial pancreatogram (or PD image from cross-sectional test – MRCP, MRI, CT scan, or EUS) with stone location and two representative final occlusion pancreatogram images will be uploaded to the REDCap database and will be reviewed by a blinded endoscopist to assess the level of stone clearance (complete or partial).

6. Standard of Care/Research Procedure

The current standard of care for the treatment of PD stones varies by region. In Europe, extracorporeal shock- wave lithotripsy (**ESWL**) is a primary method by which stones are fragmented. Once ESWL is performed, however, ERP is still performed to remove the stone fragments. In Europe, ESWL is frequently performed by gastroenterologists who can perform ERP as well.

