Subjects may withdraw from the study at any time for any reason. Subjects can also be withdrawn from the study at any time at the discretion of the investigators for breach of study protocol or emergence of an exclusion criteria (i.e. pregnancy).

The study can be stopped at any point should the Data Safety Monitoring Board (DSMB) request cessation

of the trial based on any compilation of adverse events or clear demonstration of superiority of one technique. Similarly, should the interim analysis reveal futility in that the study hypothesis is deemed unprovable within the constraints of the study, the study may be stopped. The study will also be stopped once the intended sample size goal is reached and 6-month follow-up has been obtained. Lastly, the study can be stopped should study costs exceed the allotted budget.

8. Data Collection Tool

A comprehensive system has been previously developed at this institution, and will support the data collection and reporting needs of this project which includes:

- (i) streamlining data collection from the participating centers,
- (ii) creating a secure database from which statistical analysis can be performed. Data will be stored at the University of Colorado instance of REDCap15, which resides on a local secure server. Data regarding stone clearance rates and adverse events will be entered by investigators at each center. Using an Application Programming Interface (API), data can be transferred to and from REDCap to SAS software (v.9.3, SAS Institute, Cary, NC) used to export data from REDCap to SAS to conduct analysis. SAS software interfaces seamlessly with REDCap-produced syntax files (i.e. SAS code) and SAS-ready CSV (comma separated variables) data files. Results of these analyses will be imported back into REDCap, using the API, for long-term storage, reference, and further analysis. Access to these data will be controlled by a custom module and all users of the site will be required to log in. No protected health information will be collected or displayed and data stored in our HIPAA compliant serve environment to ensure privacy.

9. Data Analysis Plan

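### Sections 3 and 7 conflict on exclusion criteria found after randomisation, and no rule says how a withdrawn patient without a final pancreatogram counts in the primary analysis

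*Combined protocol and SAP*

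**What the plan says.** Two sections deal with exclusion criteria that come to light after randomisation.

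- Section 3 (Sample and Methodology): "Patients who are randomized and subsequently found to have an exclusion criteria identified will continue follow-up per study protocol".
- Section 7 (Subject and Study Stopping Criteria): subjects can be withdrawn from the study "at the discretion of the investigators for breach of study protocol or emergence of an exclusion criteria (i.e. pregnancy").

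Section 4.2 lists, as exclusion 5, "Inability to place a transpapillary pancreatic duct stent during ERP" and, as exclusion 4, "Nontraversable ansa loop with upstream stones".

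On timing, Section 5.3 states: "Randomization will occur after informed consent is obtained and prior to receiving lithotripsy". No ERP is required before that; Sections 3 and 4.1 accept imaging, endoscopic ultrasound or ERP as ways of identifying the stones. Allocation is open: "The investigator will then inform the patient which lithotripsy therapy will be subsequently performed". The only blinding described is that of the endoscopist who reviews the images (Section 5.5).

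In the PPL arm, Section 5.4 begins treatment with ERP: "Standard ERP will be performed to cannulate the PD". For both arms, Section 5.5 says: "All patients will receive an ERP at the completion or either PPL or ESWL". Section 5.4 also allows for an ERP before ESWL, but does not require one.

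Section 9 names intention-to-treat as the primary analysis and spells it out only for cross-over. Section 3 counts failure to remove any main-duct stone as treatment failure.

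**The concern.** Section 3 tells the site to keep such a patient in follow-up. Section 7, read at face value, allows the same patient to leave the study. Which rule applies is left to an investigator who knows the arm and, for exclusion 5, has just seen the technical result.

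A stent that cannot be placed is an eligibility matter if it is found before randomisation. Found afterwards, it may be the first sign that the assigned strategy is failing. If that patient is withdrawn, the final occlusion pancreatogram that determines clearance may never be obtained, and the plan does not say how to score its absence. Whether such a patient is a failure or simply missing would then be decided after the data are in. If failures are lost more often from PPL than from ESWL, the primary comparison tilts towards the trial's own hypothesis.

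**Working it through.** **1. The passages side by side**

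| Question | What the plan says |
|---|---|
| Exclusion criterion found after randomisation | Section 3: stays in follow-up. Section 7: may be withdrawn from the study. |
| Can exclusion 5 first appear after allocation? | Yes. It is observed at an ERP, and none is required before randomisation. |
| Does the person deciding know the arm? | Yes (Section 5.3). |
| Can it arise in both arms? | Yes. ERP opens PPL treatment; for ESWL the mandatory ERP is at completion and an earlier one is optional. |
| How is a withdrawn patient without a final pancreatogram counted? | Not stated. |

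Exclusion 4 may be found in the same way, but the text does not say when it is assessed, so the argument rests on exclusion 5.

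**2. The plan's own sample size**

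Inputs (Section 9): clearance 70% for ESWL and 90% for PPL, two-sided alpha 0.05, power 80%. With pooled variance and no continuity correction:

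n per arm = [1.960 × √(2 × 0.8 × 0.2) + 0.842 × √(0.7 × 0.3 + 0.9 × 0.1)]² / 0.2² = 61.6, so 62 per arm and 124 in total.

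This matches the plan. The plan then allows for 20% dropout to reach 75 per arm, so it expects some randomised patients not to contribute to the analysis.

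**3. What unequal loss of failures would do**

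Assumptions: 75 randomised per arm; true clearance 70% in both arms, so no difference; every patient removed is a failure. The numbers removed, a from PPL and b from ESWL, are assumed, because the documents give no access-failure rate.

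Apparent clearance = 0.70 × 75 / (75 − number removed) = 52.5 / (75 − number removed). For example, 52.5/71 = 73.9% and 52.5/67 = 78.4%.

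The type I error is the exact binomial probability that the uncorrected two-sided chi-squared test at 0.05 rejects, with 75 − a and 75 − b patients at those apparent rates.

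| Removed from PPL | Removed from ESWL | Apparent PPL | Apparent ESWL | Type I error |
|---|---|---|---|---|
| 0 | 0 | 70.0% | 70.0% | 4.9% |
| 2 | 0 | 71.9% | 70.0% | 5.7% |
| 4 | 0 | 73.9% | 70.0% | 8.2% |
| 8 | 0 | 78.4% | 70.0% | 20.4% |
| 4 | 2 | 73.9% | 71.9% | 6.1% |
| 8 | 4 | 78.4% | 73.9% | 9.0% |
| 4 | 4 | 73.9% | 73.9% | 5.2% |
| 8 | 8 | 78.4% | 78.4% | 5.0% |

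What drives the error is the imbalance between the arms. In the 8-and-4 row, 8.5 of the 9.0 percentage points are rejections in favour of PPL.

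**The case against.** The strongest reply is that nothing in the plan removes anyone from the denominator. Section 7 concerns leaving the study, not leaving the analysis. Section 9 makes intention-to-treat primary. Section 3 already treats failure to remove any stone as treatment failure, and it offers cross-over after failure, with the outcome credited to the initial therapy. Applied strictly, these rules keep a patient whose duct is never accessed in the PPL arm as a failure. A reader might infer that the plan orders access failures out of the PPL denominator; the documents do not support that. What stands is a gap: the intention-to-treat set is not defined, and nothing says that the failure rule reaches a patient who was withdrawn before a final pancreatogram.

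Second, the conflict may be narrower than it looks. Section 7 speaks of a criterion emerging and gives only pregnancy, which could mean a new condition; Section 3 would then govern a failed stent. That reading is fair, but the text does not settle it, and the protocol-breach ground carries no such limit.

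Third, a reader might infer a bias confined to PPL. The documents do not support that either. Every ESWL patient also has an ERP, one may precede ESWL, and some access problems may be known from an ERP before randomisation. That the criterion surfaces more often at the start of PPL is a plausible inference from the order of procedures, not a stated fact. With equal removal the error stays near 5%.

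**Conclusion.** The point holds in conditional form. Sections 3 and 7 give conflicting instructions, at least on their face, about patients found after randomisation to meet an exclusion criterion. The discretion lies with investigators who know the allocation, and one such criterion is itself a technical failure visible only at ERP. Because the intention-to-treat set is undefined and a missing final pancreatogram has no scoring rule, these failures could drop out of the primary analysis.

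The size depends on how many are lost and from which arm, neither of which the documents give. Under the stated assumptions, the type I error runs from about 5% when losses are equal, through 6.1% (4 PPL, 2 ESWL) and 9.0% (8 PPL, 4 ESWL), to 8.2% and 20.4% when 4 or 8 failures are lost from PPL only. The PPL-only rows are the extreme case and should not be read as a forecast. The gap should be closed before the data are analysed, since a rule chosen after the results are known would carry little weight.

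**What to change.** 1. **Sections 3 and 7.** Reconcile them so that stopping study treatment is separate from leaving the study. A patient found after randomisation to have an exclusion criterion or a protocol breach should stay in follow-up and outcome collection unless consent is withdrawn. This concerns data collection only; when treatment should stop is a clinical matter for the investigators.
2. **Section 9.** State that every randomised patient stays in the primary denominator of the assigned arm. State also that a patient without documented complete clearance under the protocol's own definition, including one whose duct was never accessed, counts as not cleared in either arm.
3. **Reporting.** Report withdrawals by arm and reason.

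A failed stent placement should not be scored as a failure in itself. Section 3 defines clearance by the absence of stones on occlusion pancreatography and allows up to 4 sessions, so a patient whose duct is later cleared within those limits is a success under the trial's own endpoint.

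The cost is a short amendment to Sections 3 and 7 and a few sentences in Section 9, with no new procedures. Observed clearance rates may be slightly lower.
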